# 8.6 Audits and inspections

Authorized representatives of AstraZeneca, a regulatory authority, or an Institutional Review Board may perform audits or inspections at the center, including source data verification. The purpose of an audit or inspection is to systematically and independently examine all study-related activities and documents, to determine whether these activities were conducted, and data were recorded, analysed, and accurately reported according to the protocol, GCP, guidelines of the ICH, and any applicable regulatory requirements. The investigator will contact AstraZeneca immediately if contacted by a regulatory agency about an inspection at the center.

#### 9. STUDY MANAGEMENT

# 9.1 Pre-study activities

Before the first volunteer is entered into the study, it is necessary for a representative of AstraZeneca to visit the investigational study site to:

- Determine the adequacy of the facilities
- Determine availability of appropriate volunteers for the study
- Discuss with the investigator(s) (and other personnel involved with the study) their responsibilities with regard to protocol adherence, and the responsibilities of AstraZeneca or its representatives. This will be documented in a Clinical Study Agreement between AstraZeneca and the investigator

# 9.2 Training of study site personnel

Before the first volunteer is entered into the study, an AstraZeneca representative will review and discuss the requirements of the Clinical Study Protocol and related documents with the investigational staff and also train them in any study specific procedures and system(s) utilized.

The Principal Investigator will ensure that appropriate training relevant to the study is given to all of these staff, and that any new information relevant to the performance of this study is forwarded to the staff involved.

The Principal Investigator will maintain a record of all individuals involved in the study (medical, nursing and other staff).

# 9.3 Monitoring of the study

During the study, an AstraZeneca representative will have regular contacts with the study site, including visits to:

• Provide information and support to the investigator(s)

- Confirm that facilities remain acceptable
- Confirm that the investigational team is adhering to the protocol, that data are being accurately and timely recorded in the eCRFs, that biological samples are handled in accordance with the Laboratory Manual and that study drug accountability checks are being performed
- Perform source data verification (a comparison of the data in the eCRFs with the volunteer's medical records at the hospital or practice, and other records relevant to the study) including verification of informed consent of participating volunteers. This will require direct access to all original records for each volunteer (eg, clinic charts)
- Ensure withdrawal of informed consent to the use of the volunteer's biological samples is reported and biological samples are identified and disposed of/destroyed accordingly, and the action is documented, and reported to the volunteer

The AstraZeneca representative will be available between visits if the investigator(s) or other staff at the center needs information and advice about the study conduct.

#### 9.3.1 Source data

Refer to the Clinical Study Agreement for location of source data.

## 9.4 Study agreements

The Principal Investigator at each/the center should comply with all the terms, conditions, and obligations of the Clinical Study Agreement, or equivalent, for this study. In the event of any inconsistency between this Clinical Study Protocol and the Clinical Study Agreement, the terms of Clinical Study Protocol shall prevail with respect to the conduct of the study and the treatment of volunteers and in all other respects, not relating to study conduct or treatment of volunteers, the terms of the Clinical Study Agreement shall prevail.

Agreements between AstraZeneca and the Principal Investigator should be in place before any study-related procedures can take place, or volunteers are enrolled.

#### 9.4.1 Archiving of study documents

The Investigator follows the principles outlined in the Clinical Study Agreement.

# 9.5 Study timetable and end of study

The end of the study is defined as 'the last visit of the last volunteer undergoing the study.'

The study is expected to start in Q3 2014 and to end by Q1 2015.

The study may be terminated if the study procedures are not being performed according to GCP, or if recruitment is slow. AstraZeneca may also terminate the entire study prematurely if concerns for safety arise within this study or in any other study with AZD9291.

#### 10. DATA MANAGEMENT

Data management will be performed by

Adverse events and medical/surgical history will be classified according to the terminology of the latest version of the Medical Dictionary for Regulatory Activities (MedDRA). Medications will be classified according to the AstraZeneca Drug Dictionary. All coding will be performed by

Data queries will be raised for inconsistent, impossible or missing data. All entries to the study database will be available in an audit trail.

The data will be validated as defined in the Data Management Plan. Quality control procedures will be applied to each stage of data handling to ensure that all data are reliable and have been processed correctly.

When all data have been coded, validated, signed, and locked, clean file will be declared. Any treatment revealing data may thereafter be added and the final database will be locked.

Data associated with biological samples will be transferred to laboratories internal or external to AstraZeneca.

#### 11. EVALUATION AND CALCULATION OF VARIABLES

# 11.1 Calculation or derivation of safety variable(s)

### 11.1.1 Calculation of change from baseline

Change-from-baseline variables will be calculated for the safety variables listed below, as the post treatment value minus the value at baseline. The baseline values will be as follows:

- Clinical laboratory tests: last measureable value taken prior to first dose
- Vital signs: last measureable value taken prior to first dose
- Paper 12-lead ECG: last measureable value taken prior to first dose

If a volunteer is missing the baseline collection, the previous nonmissing evaluation will become the baseline value. If no baseline or previous-to-baseline evaluations exist, then the baseline value will be treated as missing and no change-from-baseline value will be calculated.

#### 11.1.2 Other significant adverse events (OAE)

During the evaluation of the AE data, an AstraZeneca medically qualified expert will review the list of AEs that were not reported as SAEs or discontinuations of IP due to AEs (DAEs). Based on the expert's judgement, significant AEs of particular clinical importance may, after consultation with the Global Patient Safety Physician, be considered OAEs and reported as such in the CSR. A similar review of laboratory/vital signs/ECG data will be performed for identification of OAEs.

## 11.2 Calculation or derivation of pharmacokinetic variables

The sample bioanalysis will be performed by
with actual PK sampling times will be performed by
analysis will be the responsibility of the pharmacokineticist at
The actual sampling times will be used in the final PK parameter calculations. Nominal sampling times will be used for interim PK parameter calculations.

Pharmacokinetic parameters will be derived using noncompartmental methods with Phoenix® WinNonlin® Version 6.3, or higher, (Pharsight Corp, St. Louis, Missouri, USA) and/or SAS® version 9.2, or higher (SAS Institute, Inc, Cary, North Carolina, USA). All descriptive and inferential statistical computations will be performed using SAS® version 9.2, or higher.

Where possible the following PK parameters will be determined for AZD9291 and its metabolites, AZ5104 and AZ7550, as appropriate following dosing on Day 5 in Period 1 and Day 1 in Period 2:

- Maximum plasma concentration (Cmax)
- Time to maximum plasma concentration  $(t_{max})$
- Lag time before observation of quantifiable analyte concentrations in plasma ( $t_{lag}$ )
- Terminal rate constant  $(\lambda_z)$
- Terminal half life  $(t_{\frac{1}{2}})$
- Area under the plasma concentration-time curve from zero to the time of the last quantifiable concentration ( $AUC_{0-t}$ )
- Area under the plasma concentration-time curve from zero to 72 hours (AUC0-72)
- Area under the plasma concentration-time curve from zero to infinity (AUC)
- Apparent plasma clearance (CL/F) for AZD9291 only
- Apparent volume of distribution  $(V_7/F)$  for AZD9291 only

• Metabolite to parent ratio (calculated as AZ5104/ AZD9291 and AZ7550/ AZD9291 for both  $C_{max}$  and AUC). These ratios will be adjusted for differences in molecular weight (AZD9291 = 499.61 AZ5104 and AZ7550 = 485.59)

# 12. STATISTICAL METHODS AND SAMPLE SIZE DETERMINATION

## 12.1 Description of analysis sets

## 12.1.1 Safety analysis set

All volunteers who received at least 1 dose of omeprazole or AZD9291 and for whom any postdose data are available will be included in the safety population.

#### 12.1.2 Pharmacokinetic analysis set

The PK analysis set will include all healthy volunteers who receive at least 1 dose of the IP and have at least 1 postdose PK measurement without important protocol deviations/violations or events thought to significantly affect the PK of the IP (eg, healthy volunteer vomited at or before 2 times median tmax, wrong dose administered, prohibited concomitant medication, etc). The PK scientist will evaluate the strategy for dealing with data affected by protocol deviations before any formal statistical analysis is performed.

# 12.2 Methods of statistical analysis

# 12.2.1 General principles

Statistical analyses will be performed per standard operating procedures using SAS® Version 9.2 or higher and, where appropriate, additional validated software.

A healthy volunteer who withdraws prior to the last planned observation in the study period will be included in the analyses up to the time of discontinuation. No adjustment or imputation will be utilized for missing values or for healthy volunteers who withdraw prior to completing the study, or will analyses be restricted to healthy volunteers with complete data.

Data from nonvalid healthy volunteers (healthy volunteers excluded from the analysis set[s]), which are recorded in the database, will only be presented in listings.

The analysis of data will be based on different subsets according to the purpose of analysis, ie, for safety and PK, respectively.

All derived variables/parameters will be rounded for reporting purposes in the summary tables and healthy volunteer listings, as per standard operating procedures.

#### 12.2.2 Subject characteristics

Continuous variables will be summarized using descriptive statistics (n, mean, standard deviation [SD], minimum, median, maximum). Categorical variables will be summarized in frequency tables (frequency and proportion).

#### 12.2.3 Safety and tolerability

Safety data include AEs, vital signs, physical examinations, ophthalmologic examination, electrocardiograms, and clinical laboratory assessments.

All safety data (scheduled and unscheduled) will be presented in the data listings. Continuous variables will be summarized using descriptive statistics (n, mean, SD, minimum, median, maximum) by treatment. Categorical variables will be summarized in frequency tables (frequency and proportion) by treatment.

All AEs that occur following the first dose of omeprazole in Period 1 will be included in the analyses of AEs, including episodes that occur during the wash-out period.

All available data from healthy volunteers in the safety analysis set will be included in the safety analyses.

All AEs will be collected for each healthy volunteer from Day -1, Treatment period 1 (Visit 2) until the follow-up visit (Visit 15). All SAEs will be collected for each healthy volunteer from the time when informed consent is obtained until the follow-up visit (Visit 15).

Adverse events will be listed for all healthy volunteers with AEs that occur before administration of the IP indicated on the listing. The number of AEs experienced following administration of the IP will be summarized in tables using the MedDRA (Version 13.0 or higher) system organ class and preferred term. These summary tables will also be produced with severity and causality of AEs added as additional classification factors. The number of AEs overall, SAEs, OAEs, AEs that lead to withdrawal, AEs of severe intensity, and causally-related AEs will be summarized. Any AE occurring postdose will be considered associated with the last dose of the IMP taken. Any AE occurring on Day -1, Treatment period 1 (Visit 2) will not be included in the summaries.

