In Part A of the study (3 formulation comparison), 10/16 (62.5%) volunteers reported an AE during the 9-week duration of the study, with no SAEs, deaths or AEs leading to discontinuation. Only influenza was reported by more than 1 volunteer (n=3, 19%). No events were considered related to administration of AZD9291.

In Part B of the study (food effect), 6/16 (37.5%) volunteers reported an AE during the 6-week duration of the study, with no SAEs or deaths, and 1 AE leading to discontinuation after the first dosing period (alanine aminotransferase [ALT] increased). One further volunteer was lost to follow up after the first dosing period. Only upper respiratory tract infection was reported by more than 1 volunteer (n=2, 13%). Only 1 event of ALT increased was assessed as causally related to administration of AZD9291, which was an increase to a maximum value of 101 U/L on Day 15 after single dose of AZD9291 with no changes in aspartate aminotransferase (AST), bilirubin or alkaline phosphatase over this period. Other than the single event of ALT increased, no volunteers had any other clinically significant abnormal vital signs, clinical laboratory parameters or changes in electrocardiogram (ECG) parameters, including the QT interval corrected for heart rate (QTc).

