# 3.1 Overall study design and flow chart

This is a Phase I, open-label, 2-period fixed sequence design study to evaluate the interaction of AZD9291 with omeprazole in approximately 50 healthy, adult male volunteers. The study will be performed at up to 2 sites in the USA.

Volunteers will receive Treatment A in Period 1 and Treatment B in Period 2; the dose of AZD9291 in Period 1 and the dose of AZD9291 in Period 2 will be separated by a washout of at least 21 days (the washout will not be more than 5 weeks).

Treatment A: On Days 1 through 4, omeprazole will be administered in the morning

after a 10-hour fast with 240 mL of water 1 hour before eating breakfast. On Day 5, omeprazole will be administered together with AZD9291 with

240 mL of water following an overnight fast of 10 hours and the volunteers will remain fasting from food until 4 hours postdose.

Treatment B: Volunteers will receive AZD9291 in the morning on Day 1 with 240 mL

of water following an overnight fast of 10 hours. Volunteers will remain

fasting from food after dosing until 4 hours postdose.

The omeprazole and AZD9291 will be administered with 240 mL of water in the morning after a 10-hour fast. On Days 1 through 4 in Period 1, volunteers will remain fasting from food for at least 1 hour after omeprazole administration; on Day 5 of Period 1 and Day 1 of Period 2, volunteers will remain fasting from food after dosing until 4 hours postdose. Apart from the water given at dosing, volunteers will be fasted from water from 1 hour prior to dosing until 1 hour after dosing on each occasion.

The study will consist of up to 15 visits depending on whether the final PK sample of Period 1 is collected as the predose PK blood sample for Period 2 or whether a separate visit is required for the predose PK blood sample. Details and timing of assessments are included in Table 1 and Table 2. The screening visit (Visit 1) will be conducted within 28 days of Visit 2. Following full written informed consent, healthy volunteers will be enrolled into the study and screened for eligibility.

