In Period 1 the volunteers will report to the clinic on Day -1 (the day prior to first dose of omeprazole) and remain resident until the 48-hour postdose (relative to AZD9291 administration on Day 5) monitoring and evaluations have been performed on Day 7. The volunteers will return to the clinic for outpatient visits on Days 8, 10, 12, 14 and 19. The Day 26 postdose assessments may be used as the Day -1 predose assessments for Period 2 if an exact 21 day washout is used between AZD9291 doses in Period 1 and Period 2. AZD9291 concentrations obtained over the first 72 hours in Period 1 will be evaluated to determine if exposure limit criteria for a given volunteer and/or a group of dosed volunteers are met or exceeded prior to AZD9291 administration in Period 2. Volunteer(s) exceeding PK exposure limits will be withdrawn.

[figure not shown]
In Period 2 the volunteers will report to the clinic on Day -1 and remain resident until 48-hour postdose (relative to AZD9291 administration) monitoring and evaluations have been performed on Day 3. The volunteers will return to the clinic for outpatient visits on Days 4, 6, 8, 10, 15 and 22. A final follow-up visit (Visit 15) will be performed 7 to 14 days after the last PK blood sample in Period 2.

Safety assessments will include monitoring of AEs and concomitant medications; clinical laboratory tests (hematology, clinical chemistry and urinalysis); measurement of vital signs (supine blood pressure and pulse); ECGs; physical examinations; screening for drugs of abuse, alcohol and cotinine; and ophthalmologic examinations.

Blood samples for the determination of AZD9291 and metabolite (AZ5104 and AZ7550) concentrations will be collected prior to dosing of AZD9291 and serially postdose for 21 days in each treatment period. The PK profile from 0 to 72 hours post AZD9291 dose will be assessed after Period 1 and Period 2 and any volunteer with exposures exceeding the PK limits (Section 5.8) will be withdrawn and may be replaced if required to ensure 40 evaluable volunteers complete. For a volunteer to be evaluable the volunteer must have completed the required PK collections for both study periods without important protocol deviations and events.

The overall study flow chart and study is presented in Figure 1.

Figure 1 Study flow chart

- a Volunteers will be admitted into the clinic on Day -1 in both periods.

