- b Each AZD9291 dosing day will be a minimum of 21 days (504 hours) apart (the washout will not be more than 5 weeks).
- Note where the washout is 21days, Day 26of Period 1 will coincide with Day-1 of Period 2 (ie, the 504-hour postdose PK assessment from Period 1 will be collected on Day -1 of Period 2); where the washout is slightly longer volunteers may return to the clinic for an additional visit prior to admission to Period 2 to allow for the collection the PK sample.
- Treatment A: On Days 1 through 4, omeprazole will be administered in the morning after a 10-hour fast with 240 mL of water 1 hour before eating breakfast. On Day 5, omeprazole will be administered together with AZD9291 with 240 mL of water following an overnight fast of 10 hours and the volunteers will remain fasting from food until 4 hours postdose.
- e Treatment B: Volunteers will receive AZD9291 in the morning on Day 1 with 240 mL of water following an overnight fast of 10 hours. Volunteers will remain fasting from food after dosing until 4 hours postdose.

Table 1 Study plan

Visit	1	2 t	o 7		8	to 13	14
Assessment	Screening	Period 1 ≥21 day washout b		Period 2		Follow up visit	
Day	-28 to -2	-1	1 to 26		-1	1 to 22	
Residential period (Day)		X	1 to 7		X	1 to 3	
Nonresidential visit	X		X l			$\mathbf{X}^{\mathbf{l}}$	X
Informed consent	X						
Informed consent, pharmacogenetic m	X						
Demography	X						
Inclusion/exclusion criteria	X	X					
Medical history	X	X					
Clinical laboratory tests a	X	X	X		X	X	X
Serology	X						
Height and body mass index	X						
Weight	X	X			X		
Urinary drug, alcohol breath test, and cotinine screen c	X	X			X		
Ophthalmological assessment	X d						
Physical examination e	X	X			X		X
Vital signs (supine blood pressure and pulse) f	X	X	X		X	X	X
12-lead electrocardiogram g	X	X	X		X	X	X
AZD9291 administration h			X			X	
Omeprazole administration i			X				
AZD9291 PK blood sampling j			X		X	X	X
Concomitant medications	X	X	X	X	X	X	X
Adverse event recording k		X	X	X	X	X	X

a Clinical laboratory tests: Period 1, Days -1, 5 (pre-dose), 7, 12 and 19; Period 2; Days -1, Days 3, 8, 15 and 22.

- b Each AZD9291 dosing day will be a minimum of 21 days (504 hours) apart (the washout will not be more than 5 weeks).

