## **6.2.2** Follow-up procedures

A medical examination will be performed on Day 55. This will be similar to the one performed at the pre-entry visit and will include a complete physical examination, assessment of any AEs and concomitant medication, vital signs, a resting 12-lead ECG, and safety laboratory tests.

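### Last-dose attribution gives the by-treatment adverse event tables observation windows of unequal and variable length, and the direction of the imbalance depends on the washout

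*Protocol*

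**What the plan says.** Protocol Section 12.2.3 asks for frequencies and proportions by treatment. It includes AEs from the first omeprazole dose onwards, washout included, and collects them until the follow-up visit. The attribution rule is: "Any AE occurring postdose will be considered associated with the last dose of the IMP taken". No end of window and no adjustment for time observed is given.

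The schedule in Section 3.1 fixes how long each treatment stays the last one taken:

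- Between the two AZD9291 doses: "Each AZD9291 dosing day will be a minimum of 21 days (504 hours) apart", with an upper limit of five weeks.
- After the Period 2 dose, blood is drawn "serially postdose for 21 days in each treatment period", and then: "A final follow-up visit (Visit 15) will be performed 7 to 14 days after the last PK blood sample in Period 2".

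Two further statements bear on the windows. Section 3.1 starts Treatment A with omeprazole alone on Days 1 to 4. Section 12.2.3, however, counts tabulated AEs from the IP and attributes them to the last IMP dose, and the synopsis lists omeprazole as non-investigational. The column for AEs on those four days is therefore not defined. Section 6.2.2 also times the follow-up differently: "A medical examination will be performed on Day 55".

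**The concern.** Most AEs in the earlier healthy-volunteer study were not judged related to AZD9291. Section 1.3.1 reports none related in Part A and one in Part B, and the only terms seen in more than one volunteer were influenza and upper respiratory tract infection. Events of that kind accumulate with time observed. When two columns of a by-treatment table cover different numbers of days, they can differ with no drug effect at all. The Period 1 window also varies between volunteers with the washout each one happens to have. A reader of the tables could take such a gap for a property of the combination, and Section 12.2.3 gives nothing that would show otherwise.

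**Working it through.** The protocol states no AE window length or expected AE proportion, so there is no figure of its own to reproduce. The schedule is consistent on the minimum gap: 504 h / 24 = 21 days.

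**Step 1. Windows, from Section 3.1.** Combination: from the Period 1 AZD9291 dose to the Period 2 dose, 21 to 35 days. AZD9291 alone: last sample at 21 days plus 7 to 14 days, so 28 to 35 days. If omeprazole-only Days 1 to 4 count as Treatment A, add 4 days: 25 to 39. The one-day tolerance on late samples (Section 6.4.1) is ignored.

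| Washout (days) | Combination (days) | Alone (days) | Ratio alone/combination | Combination with Days 1–4 (days) | Ratio |
|---|---|---|---|---|---|
| 21 | 21 | 28–35 | 28/21 = 1.33 to 35/21 = 1.67 | 25 | 28/25 = 1.12 to 35/25 = 1.40 |
| 28 | 28 | 28–35 | 28/28 = 1.00 to 35/28 = 1.25 | 32 | 28/32 = 0.88 to 35/32 = 1.09 |
| 35 | 35 | 28–35 | 28/35 = 0.80 to 35/35 = 1.00 | 39 | 28/39 = 0.72 to 35/39 = 0.90 |

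**Step 2. Background rates, from Section 1.3.1.** Part A: "10/16 (62.5%) volunteers reported an AE during the 9-week duration of the study". Part B: 6 of 16 over 6 weeks. Assume a constant rate and treat all these events as background:

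- Part A: −ln(1 − 10/16)/63 = 0.0156 per day
- Part B: −ln(1 − 6/16)/42 = 0.0112 per day

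**Step 3. Expected share with at least one AE**, 1 − exp(−rate × days):

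| Days | Part B rate | Part A rate |
|---|---|---|
| 21 | 20.9% | 27.9% |
| 25 | 24.4% | 32.2% |
| 28 | 26.9% | 35.3% |
| 35 | 32.4% | 42.0% |
| 39 | 35.4% | 45.5% |

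**Step 4. Gap from window length alone.**

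- 21-day washout, counted from AZD9291: from 26.9 − 20.9 = 6.0 to 42.0 − 27.9 = 14.1 points, fewer with the combination.
- 21-day washout with Days 1–4: from 26.9 − 24.4 = 2.5 to 42.0 − 32.2 = 9.8 points, same direction.
- 35-day washout, counted from AZD9291: zero if follow-up is at 35 days. If it is at 28 days, 32.4 − 26.9 = 5.5 to 42.0 − 35.3 = 6.7 points, now more with the combination.
- 35-day washout with Days 1–4: at most 35.4 − 26.9 = 8.5 to 45.5 − 35.3 = 10.2 points, more with the combination.

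**Step 5. Common window.** Cutting both treatments at 21 days after AZD9291 gives 20.9% (Part B rate) or 27.9% (Part A rate) in each column, whatever the washout.

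**Step 6. Follow-up timing.** Take Day 55 as counted from Period 1 Day 1.

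- 21-day washout: Period 2 dose on study Day 5 + 21 = 26, last sample on Day 47, follow-up under Section 3.1 on Days 54 to 61. Day 55 fits and is 29 days postdose.
- 22-day washout: follow-up on Days 55 to 62. Day 55 just fits.
- 35-day washout: dose on Day 40, last sample on Day 61, follow-up on Days 68 to 75. Day 55 would be 15 days postdose, before the last sample.

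The two statements of follow-up timing agree only at a washout of about 21 to 22 days.

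**The case against.** The strongest reply is that nothing formal depends on these tables. The safety objective is to examine the combination and names no contrast with AZD9291 alone. The analysis is descriptive, with no test or decision rule. AEs are also tabulated by causality, which would filter out most background infections, and last-dose attribution is a common convention in multi-period studies. All of this stands, and it limits the harm to how the by-treatment tables are read. It does not remove the problem: the last-dose rule is set in the protocol itself, so an analysis plan that follows it inherits the unequal windows.

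A reader might go further and infer that the rule makes the combination look safer. The documents do not support a fixed direction. The permitted washouts run from 21 to 35 days, no distribution is given, and at 35 days the combination window is never the shorter. Section 12.2.3 also includes AEs from the omeprazole-only days, which may lengthen the combination window. The planned withdrawal of about 20% (Section 12.3) works against that inference for raw event counts. With all withdrawals before the Period 2 dose and a 21-day washout, Period 1 gives 50 × 21 = 1050 volunteer-days (50 × 25 = 1250 with Days 1–4), against 40 × 28 = 1120 to 40 × 35 = 1400 in Period 2.

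A reader might also quote 14 points as the expected gap. That figure combines the shortest washout, the latest follow-up, the higher rate and the exclusion of Days 1 to 4.

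**Conclusion.** The concern holds as a flaw in the descriptive safety tables. The windows differ by design and vary between volunteers, and the column for AEs on Period 1 Days 1 to 4 is undefined. At a 21-day washout the imbalance favours the combination by about 6 to 14 points (2.5 to 10 with Days 1–4). At 35 days it vanishes or reverses by up to about 5 to 7 points (8 to 10 with Days 1–4, where the combination window is always the longer).

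These sizes rest on a constant AE rate and on the earlier study's events standing in for background. Those rates come from two groups of 16, and two Part B volunteers left after the first dose, so that rate may be slightly low. The primary pharmacokinetic conclusion is untouched. The change is worth making because it is cheap.

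**What to change.** In Section 12.2.3, base the by-treatment AE incidence tables on onset from each AZD9291 dose to 21 days (504 h) after it. That window exists in both periods at every permitted washout. On the capsule half-lives in Section 3.2 it spans 504/52.72 = 9.6 mean half-lives of AZD9291 and 504/73.21 = 6.9 of AZ7550. The one related event in the earlier study peaked on Day 15, inside the window.

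Give separate columns to omeprazole-only AEs (Period 1 Days 1 to 4) and to AEs after 21 days (washout or follow-up). Keep the overall all-AE summary and the listings, so that no event is lost. State which product the terms IP and IMP cover in the attribution rule. Reconcile the follow-up timing in Sections 3.1 and 6.2.2.

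Cost: a few sentences and some extra table programming. AE start date and time are already collected (Section 6.3.3), so no new data or visits are needed. The downside is slightly fewer events in the by-treatment columns.
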